Protocol Title: Methadone Demonstration Project

NCT03134703

Protocol v5: 02.02.2018

JHM IRB - eForm A – Protocol

- **Use the section headings to write the JHM IRB eForm A, inserting the appropriate material in each. If a section is not applicable, leave heading in and insert N/A.**
- **When submitting JHM IRB eForm A (new or revised), enter the date submitted to the field at the top of JHM IRB eForm A.**

1. Abstract

- a. Provide no more than a one page research abstract briefly stating the problem, the research hypothesis, and the importance of the research.

The Problem:

Infants who are born to mothers taking or abusing opiates frequently suffer from neonatal abstinence syndrome (NAS) after birth. They often have withdrawal symptoms which can be life-threatening if untreated. The American Academy of Pediatrics (AAP) recommends non-pharmacologic treatment as first-line therapy, followed by opioid replacement for severe cases. The pharmacologic treatment usually takes place within the hospital setting. Such approach often incurs prolonged hospitalization and significant financial burden. It also creates barriers to adequate maternal/infant bonding with potential deleterious consequences for the infant's long term emotional and societal outcomes.

The Research Hypothesis: Among Neonatal Intensive Care Unit (NICU) infants diagnosed with NAS and requiring pharmacological treatment, those who are treated with methadone will have a shorter Length of Stay (LOS) of less than 15 days as compared to the average length LOS of 25 days of NAS infants admitted in recent years at Johns Hopkins All Children's Hospital (JHACH) NICU.

The Importance of the Research:

Infants suffering from NAS are historically cared for in the hospital setting and are not discharged home until all narcotic medications have been weaned off. Such prolonged hospital stay invariably equates to prolonged separation of mother and baby. Consequently, infants suffer from the absence of a care giver who could provide constant comforting techniques which are the mainstay of treatment of infants with NAS. This in turn leads to further prolongation of the hospital stay and impaired mother-infant bonding.

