This demonstration project has the potential to improve short and long term outcome of infants suffering from NAS while decreasing the cost of their care. It aims at doing so by 1) reaching out to qualifying mothers prior to delivery; 2) empowering those mothers during their infant hospital stay by further educating them on NAS and means of comforting and easing their infant's withdrawal symptoms; 3) discharging infants home while still on narcotic treatment under very close medical supervision until complete weaning is achieved; 4) ensuring a safe home environment and healthy maternal involvement throughout withdrawal and for a year after cessation of medical treatment.

Principal Investigator: [name], MPH

Application Number: IRB00107690

2. Objectives

Primary Objective: Compare the LOS of NICU infants with NAS treated with methadone with historical data and a comparison group of NICU NAS infants treated with a different narcotic agent.

Secondary Objectives:

- 1) Compare maternal bonding between methadone treated infants and those treated with a different narcotic,
- 2) Assess if methadone treatment leads to decreased maternal depressive symptomatology as compared to treatment with other narcotics;
- 3) Study whether methadone treatments leads to safer transition to home with no readmissions to the hospital within 30 days for NAS-related reasons;
- 4) Compare proportions of children who gain weight (greater than 15% above birth weight) at 30 days of age between methadone treated and non-treated infants;
- 5) Compare the incidence of providing breast milk (> 50% of nutritional needs) at 30 days of age between methadone treated and non-treated infants;
- 6) Assess the age appropriate infant development at 4, 8 and 12 months of age among the methadone treatment group;
- 7) Determine the response percentage of mothers who are screened as eligible by PAR officials and who agree to participate in the demonstration project;
- 8) Assess the drop out percentage of mothers who agree to participate but do not follow through with home discharge for continued care;
- 9) Quantitate the proportion of mothers who feel comfortable with home care of their infant at discharge;
- 10) Monitor the readiness of mothers to assess infant on 3 to 4 hours intervals while at home;
- 11) Determine the compliance rate with the Johns Hopkins All Children's Hospital (JHACH) pediatrician visits.

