NAS is manifested by central nervous system irritability (high pitch and inconsolable crying, irritability and sleep disturbances), autonomic nervous system over-reactivity (sweating, yawning, sneezing), gastrointestinal manifestations (poor feeding, emesis and loose stools) and respiratory distress (tachypnea and nasal congestion) (Finnegan 1975; Finnegan, 1976; Kaltenbach, 1986; Desmond 1975). The standard of care is to treat these infants with a slow taper of opioid but to date there is no established gold standard for that taper (Cochrane, 2010). The lack of high-quality research in the treatment of NAS has led to wide variations in medications and protocols (Patrick, 2014; O'Grady, 2009; Sarkar, 2006) and data on changes in the utilization of NICU resources in the treatment of affected infants are lacking (Tolia, 2015).

For the time frame July 1, 2013 through September 30, 2014, 300 infants with NAS have been cared for at the Johns Hopkins All Children's Hospital (JHACH) NICU with an average length of stay of 30 days. The average length of stay has recently decreased to 22-25 days with implementation of strict management guidelines and protocols. Accounting for an average daily cost of \$2062.50, the burden translates into medical costs averaging \$48,468.75 per infant. With the proposed model involving methadone treatment, we anticipate at most 14 days of care in the NICU at a cost of \$28,875.00, followed by 10 days of home care at an anticipated cost of \$190/day for a total cost of \$30,775. This is an anticipated reduction in cost of \$17,693.75 per patient.

The prolonged stay has other social and medical impacts – including limitation in parental interaction and bonding, exposure to nosocomial infections, and taking up valuable resources both in terms of personnel and equipment. Once discharged home, these infants are often exposed to inconsistent caregiving, family instability, out of home placements, chronic stress, abuse, neglect and poverty – all of which affect their health and development, thus incurring even greater societal costs. To date, there are no published data on the in-home pharmacologic treatment of these infants.

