JHACH admitted and average of 131 NAS infants in recent years who required pharmacological treatment for NAS. Approximately 30% of those mother/infant dyads were residents of PAR. We anticipate to enroll 25 mother/baby dyads into the methadone treatment group and 25 mother/baby dyads into the control group for a total of 100 participants. Both the mother and infant are research participants. Those infant participants are defined as 1) needing methadone or other opiate treatment, 2) transitioning to home care, and 3) successfully weaning off medication.

This number has been extrapolated taken into account the following projections/assumptions: 1) not all mothers staying at PAR will meet criteria for participation, and 2) polydrug use may be discovered at the time of delivery thus excluding from participation, and 3) 20-40% of infants enrolled may need adjunct second line therapy.

b. Blinding, including justification for blinding or not blinding the trial, if applicable.

This is a demonstration study with no blinding of subjects involved.

c. Justification of why participants will not receive routine care or will have current therapy stopped.

All infants will continue to receive routine hospital care. Methadone treatment is approved by the FDA, and endorsed by the AAP for inpatient and outpatient treatment of infants with NAS. While methadone is not used as the standard of care at JHACH NICU for infants with NAS at birth, it is still used for later iatrogenic withdrawal in the NICU and other intensive care units in the hospital.

d. Justification for inclusion of a placebo or non-treatment group. N/A Will need to justify this as a comparison groups has been included

e. Definition of treatment failure or participant removal criteria.

As delineated above, infants will be off-treatment from the demonstration project if 1) they require the addition of a second-line of pharmacological treatment or 2) they require re-admission to the

Principal Investigator: [name], MPH

Application Number: IRB00107690

hospital. Data will still be collected until final hospital discharge for these infants and the maternal assessments of bonding and depression will remain ongoing. .

Other Indications for participant off-study:

- a. Parent withdraws informed consent at any time
 - b. Infant transfers to another hospital.
 - c. Infant experiences an unexpected adverse event deemed related to study intervention

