- a. **Primary outcome variable:** Length of Stay (LOS)

- b. **Additional outcomes of interest to be examined:**

- 1) Maternal bonding measured by the Postpartum Bonding Questionnaire (PBQ);
- 2) Depressive symptomatology measured by Edinburgh Postnatal Depression Scale (EPDS);
- 3) Hospital readmission within 30 days;
- 4) Weight gain of greater than 15% above Birth Weight at 30 days of age;
- 5) Age appropriate development as screened by the Ages and Stages questionnaires.

- c. **Statistical plan including sample size justification and interim data analysis:**

Demographic and clinical characteristics of participants will be summarized using means with standard deviations (SD) or median with interquartile ranges for continuous variables and counts and percentages for categorical variables. The primary outcome, length of stay, will be summarized using mean (SD) or median and interquartile range and will be compared to the comparison group using the t-test or Wilcoxon rank sum test as appropriate. For the secondary outcomes, the scores on the postpartum bonding questionnaire or the Edinburgh Postnatal Depression Scale will be summarized using means (SD) and compared to other patients in the comparison group using independent two-sample t-test. The proportion of participants that are readmitted within 30 days or with a weight gain of greater than 15% above birth weight will be compared to the comparison group using a Chi-squared or Fishers exact test as appropriate. Among the methadone cohort, we will calculate percentage of infants with age appropriate development at 4, 8 and 12 months. We anticipate that 25 mother-child dyads in each group will be available for the study. We expect that the mean LOS in the comparison group will be around 25 days (based on historical data). This sample size will allow us to estimate differences in LOS of >4 days with sufficient power (80%) at an alpha of 0.05, assuming a standard deviation of 5 days for both groups.

Early stopping rules:

Infant: requiring therapy with a second drug

Parents: desire to remove the infant from the study at any time or when infant is transferred to another hospital.

7. Risks

- a. **Medical risks, listing all procedures, their major and minor risks and expected frequency:**

Principal Investigator: [name], MPH

Application Number: IRB00107690

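### The Accrual text defines infant participants partly by how treatment turned out, and section 6.c names no analysis set for the primary length-of-stay test

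*Combined protocol and SAP*

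**What the plan says.** In the Accrual text under study duration, the plan expects 25 mother/baby dyads per group and then states: "Those infant participants are defined as 1) needing methadone or other opiate treatment, 2) transitioning to home care, and 3) successfully weaning off medication". It adds that the number already allows for 20-40% of enrolled infants needing a second-line drug.

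Section 6.c compares LOS by t-test or Wilcoxon rank sum test. It says "We anticipate that 25 mother-child dyads in each group will be available for the study", and claims 80% power at alpha 0.05 for differences above 4 days, "assuming a standard deviation of 5 days for both groups". It names no analysis set. Its early stopping rules include "Infant: requiring therapy with a second drug", without saying whether such an infant stays in the LOS comparison.

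Other sections bear on who is analysed:

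- The hypothesis in the Abstract is that "those who are treated with methadone will have a shorter Length of Stay (LOS) of less than 15 days". The primary objective is to "Compare the LOS of NICU infants with NAS treated with methadone with historical data and a comparison group". Both speak of infants treated.
- Off-treatment Criteria (G): a methadone infant who needs phenobarbital loses discharge home on methadone. One who is readmitted is off-treatment.
- Definition of treatment failure (e): data on off-treatment infants are collected to final hospital discharge.
- Section 6.c treats readmission as an outcome: "The proportion of participants that are readmitted within 30 days".
- Section 7.d schedules safety reviews after 13 and then 12 more infants in the methadone treatment group.
- The note on screen failures removes only infants who need no drug treatment.

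**The concern.** Going home and weaning successfully are results of treatment. If they decide who counts as a participant, and participants are the infants analysed, the primary comparison is conditioned on success. The off-treatment rules are written for methadone infants, so the exclusion could fall only or mainly on that group. Infants who need phenobarbital cannot go home on methadone, so they are the likeliest long stays. Removing them would lower the methadone mean.

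The definition also fits the comparison group poorly. The Background uses home care for the nursing service that follows early discharge on methadone ("followed by 10 days of home care"). On that meaning no comparison infant could qualify, although the definition covers other opiates.

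The study is unblinded and non-randomised. With no set named, the choice could be made after the data are seen. At stake are the size of the LOS difference and, for some inputs, whether the methadone mean falls below 15 days.

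**Working it through.** **The plan's own figure.** Inputs from 6.c: difference 4 days, SD 5, alpha 0.05 (taken as two-sided), power 80%. n = 2 × (1.960 + 0.842)² × 5² / 4² = 24.5, so 25 per group. Power with 25 v 25 is 80.7% by the normal formula and 79.1% by the noncentral t. The sample-size arithmetic is sound; the question is who is analysed.

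**Bias if only methadone failures are dropped.** Let p be the share failing, 0.2 to 0.4 (the plan's figure for adjunct need, used here as the failure rate). Assume LOS is normal with SD 5, and let ρ be the latent correlation between failing and LOS (not in the documents). The methadone mean falls by ρ × 5 × φ(z) / (1 − p), where z is the 1 − p normal quantile.

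- p = 0.2: φ(0.842) = 0.280, so the shift is ρ × 5 × 0.280 / 0.8 = 1.75ρ.
- p = 0.4: φ(0.253) = 0.386, so the shift is ρ × 5 × 0.386 / 0.6 = 3.22ρ.

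False positives come from simulation with no true difference: 25 methadone infants, of whom the 5 or 10 likeliest to fail are dropped, against 25 unfiltered comparison infants, two-sided t-test at 0.05. The nominal rate favouring methadone is 2.5%.

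| ρ | Shift, p = 0.2 | Shift, p = 0.4 | False positives favouring methadone, p = 0.2 | p = 0.4 |
|---|---|---|---|---|
| 0 | 0 | 0 | about 2.5% | about 2.5% |
| 0.3 | 0.5 days | 1.0 days | 5% | 8% |
| 0.5 | 0.9 days | 1.6 days | 8% | 16% |
| 1 (longest stays dropped) | 1.75 days | 3.2 days | 24% | 55% |

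With both groups filtered the same way, the shifts cancel and the rate stays close to 2.5% at ρ = 0.3 and 0.5.

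**The 15-day hypothesis.** The all-treated mean is s(1 − p) + fp, where s is the mean LOS of successes and f that of failures. Both are assumed. For f, I take 22-25 days, the unit's recent average in the Background.

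| s | p = 0.2, f = 22 to 25 | p = 0.4, f = 22 to 25 |
|---|---|---|
| 14 | 15.6 to 16.2 | 17.2 to 18.4 |
| 12 | 14.0 to 14.6 | 16.0 to 17.2 |
| 10 | 12.4 to 13.0 | 14.8 to 16.0 |

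The success-only mean is below 15 in every row; the all-treated mean is not. This table does not hold the SD at 5. The gap between the two means is p(f − s). Only s = 14 with f = 22 (gaps 0.2 × 8 = 1.6 and 0.4 × 8 = 3.2) stays within the normal-LOS limits of 1.75 and 3.22. The other rows need a wider or non-normal spread.

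**The meaning of 25.** If 25 methadone infants are treated and only successes are tested, 20 or 15 remain against 25. Power for 4 days is then 74.1% or 66.5%, against 79.1%. If instead 25 successes are wanted, 25 / 0.8 = 31.25 (32 infants) to 25 / 0.6 = 41.7 (42 infants) must start methadone. That does not match 13 + 12 = 25 in section 7.d.

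**The case against.** A reader might infer that the sponsor plans to drop failures from the LOS test. The documents do not support that. The sentence sits in the Accrual text and is not called an analysis set. Off-treatment infants are followed to final discharge, readmission is an outcome for participants, and section 7.d counts infants treated. This part of the objection stands: the defect is a conflict left open. But collecting data does not commit anyone to analysing it, and no section commits the LOS test to all treated infants.

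One-sided exclusion is also an assumption. The definition covers both groups, the second-drug line names no group, and the Background describes standard care as morphine with clonidine as adjunct. Comparison infants could therefore be removed too, and the bias depends on how unequal the filtering is. Readmitted infants may have had a short first stay, so dropping them could even work against methadone.

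It would be too strong to say that the 15-day hypothesis fails once all infants are counted. Successes at 14 days is one chosen input. The Background gives 14 days as an upper limit for NICU care, and with successes at 12 and 20% failing the all-treated mean is 14.0 to 14.6. Section 6.c plans no test against 15 days.

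The power loss is uncertain too, because the Accrual text says the 25 already allows for the 20-40%.

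Nor is the between-group test in danger at the gap the plan expects. Even the highest all-treated mean in the table, 18.4, leaves 25 − 18.4 = 6.6 days. Power for that exceeds 99% at SD 5 and is about 95% if the methadone SD widens to √(25 + 0.24 × 11²) = 7.4.

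**Conclusion.** The point holds as an unresolved conflict that should be fixed. The plan states a participant definition that depends on two post-treatment outcomes, section 6.c tests LOS without naming a set, and other sections imply a different set. That much rests on the text alone.

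The size of any bias is conditional. It needs exclusion only or mainly among methadone infants, and failures who stay longer. With 20-40% failing, SD 5, normal LOS and methadone-only exclusion, the shift is 0.5-1.0 days at a latent correlation of 0.3 and 0.9-1.6 at 0.5. It cannot exceed 1.75 days (20%) or 3.2 days (40%). False positives favouring methadone are then about 5-8% and 8-16% against 2.5%. Without correlation, or with like filtering of both groups at these correlations, the distortion essentially disappears. The 15-day conclusion can depend on the set, but only for some inputs.

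**What to change.** 1. In the Accrual text, remove the second and third conditions from the definition of infant participants, or relabel them as a completer count.
2. In 6.c, state that the primary LOS set is every consented infant who starts opioid treatment for NAS, analysed by initial treatment group regardless of adjunct therapy, readmission or home discharge.
3. State that the second-drug line under the early stopping rules does not remove an infant of either group from this analysis.
4. Reconcile what 25 per group means across the Accrual text, 6.c and 7.d.
5. For infants taken off-study (withdrawal, transfer, related adverse event), use LOS where consent and data allow, and report the number missing by group.
6. Keep the success-only result as a sensitivity analysis.

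No clinical rule changes. For off-treatment infants the cost is wording only, since their data are already collected to final discharge. Off-study infants have no stated LOS collection, so some may be missing. The LOS benefit may look smaller than in a success-only analysis. Whether readmission days count towards LOS is a separate gap that this change does not settle.

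### The plan does not say whether methadone infants who go off-treatment stay in the primary length-of-stay analysis, and two passages read literally would drop those who need a second drug

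*Combined protocol and SAP*

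**What the plan says.** Four places bear on which infants enter the LOS comparison.

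- **Accrual (under study duration and visits).** After giving 25 dyads per group, the text says: "Those infant participants are defined as 1) needing methadone or other opiate treatment, 2) transitioning to home care, and 3) successfully weaning off medication". The second and third conditions are known only after treatment has begun. On how the count was reached it says: "This number has been extrapolated taken into account the following projections/assumptions". The third item in that list is that "20-40% of infants enrolled may need adjunct second line therapy".
- **Section 6.c, Early stopping rules.** The infant line reads "Infant: requiring therapy with a second drug". The parents' line beside it reads "desire to remove the infant from the study at any time or when infant is transferred to another hospital".
- **Study Procedures, G and item e.** An infant who needs phenobarbital, or is readmitted while on methadone, is off-treatment: discharge home on methadone is no longer allowed, home nursing visits stop, and the maternal assessments continue. Item e repeats the rule ("As delineated above, infants will be off-treatment from the demonstration project if" either event occurs) and adds that data are still collected until final hospital discharge. Withdrawal of consent, transfer and a related unexpected adverse event are then listed as other off-study reasons.
- **Section 6.c, Statistical plan.** LOS "will be compared to the comparison group using the t-test or Wilcoxon rank sum test as appropriate". No analysis set is named, and nothing says whether LOS for a readmitted infant is the first stay or all hospital days.

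The one exclusion stated outright is in the note on screen failures: consented infants who never need drug treatment. Nothing similar is said of off-treatment infants.

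**The concern.** Infants who need an adjunct are not a random subset. Under G.1, phenobarbital starts only when the 24-hour Finnegan average is 11 or more despite maximal methadone, and from then on the infant cannot go home before methadone is stopped. Early discharge is the mechanism meant to shorten LOS. Leaving these infants out keeps those still eligible for early discharge and lowers the methadone mean whatever the treatment does.

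The effect on each comparison differs:

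- **Historical 25 days.** The Abstract describes this as an average over NAS infants admitted, with no limit to treatment successes. Dropping methadone failures would favour methadone.
- **Comparison group, adjunct-treated infants kept.** This also favours methadone. The Background gives morphine with clonidine adjunct as current usual care, so keeping them is plausible.
- **Comparison group, second-drug infants dropped there too.** The net direction is unknown.
- **Readmitted infants.** The direction depends on whether readmission days count in LOS. If only the first stay counts, these infants had their early discharge, and dropping them need not lower the mean.

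The study is unblinded, so without a stated rule the choice could be made with the results in view.

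**Working it through.** **1. The plan's own figure.** Inputs from Section 6.c: difference 4 days, SD 5 days, alpha 0.05 (two-sided assumed), power 80%.

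n per group = 2 x (1.960 + 0.842)^2 x 5^2 / 4^2 = 2 x 7.85 x 1.5625 = 24.5, so 25. This reproduces the plan. Power at 25 v 25 is 0.807 by the normal approximation and 0.791 by the t distribution. A one-sided test would need only 20 per group.

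**2. What the 25 counts.** The Data Safety and Monitoring Plan (Section 7.d) schedules reviews after 13 and then 12 treated infants in the methadone group, and 13 + 12 = 25. Its stopping boundaries call the 27th and 30th patients beyond the sample size. The 25 is therefore best read as infants treated.

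**3. How many could be affected.** Assume that the 20-40% in the Accrual paragraph applies to the methadone group; the documents give no figure by group and none for readmission. Then 0.20 x 25 = 5 and 0.40 x 25 = 10 infants.

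**4. Shift in the mean.** With a fraction p dropped, mean(all) = (1 - p) x mean(kept) + p x mean(dropped). Hence

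mean(all) - mean(kept) = p x [mean(dropped) - mean(kept)].

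**5. Extra days, from the protocol's rules.**
- Stability under C (Discharge home) allows discharge at Step 4 of Table 2. Steps 5, 6 and 7 need at least 3 x 2 doses x 12 h = 72 h, and Step 8 needs 24 h. The total is 96 h = 4 days, which an adjunct infant must spend in hospital.
- Section E adds 72 hours of observation off drug, done at home on the early-discharge pathway and described as matching usual hospital care. If an adjunct infant has it in hospital, the total is 4 + 3 = 7 days.

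| Extra days in dropped infants | p = 0.20 | p = 0.40 |
|---|---|---|
| 1 | 0.2 | 0.4 |
| 4 (Steps 5-8) | 0.8 | 1.6 |
| 7 (Steps 5-8 plus observation) | 1.4 | 2.8 |

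These figures assume discharge at the end of Step 4, the fastest permitted wean and otherwise equal infants. Discharge at a lower step makes them smaller; slower weaning in adjunct infants makes them larger.

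**6. Effect on the test.** If infants are dropped from the methadone group only, t-test power falls from 0.791 to 0.741 (20 v 25) or 0.665 (15 v 25). Bias matters more. In a simulation with no true effect, SD 5, and 20-40% of methadone infants dropped, an assumed correlation of 0.3 between failure and LOS gave a bias of 0.5-1.0 day and a type I error of about 6-9%. A correlation of 0.5 gave 0.9-1.6 days and about 9-16%. Zero correlation gave no bias. Nothing in the documents fixes this correlation.

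**The case against.** The strongest reply is that the plan already means to keep these infants. The Abstract and the Primary Objective define the group by treatment with methadone, not by success. Item e collects data to final hospital discharge, which is what LOS needs. Section 6.c compares readmission within 30 days, so readmitted infants are still participants there. The Accrual definition covers both groups, and comparison infants have no home-treatment pathway. Its home-care condition may therefore mean simply going home, which an adjunct infant weaned in hospital can satisfy. The second-drug line may be shorthand for G.1, since applying it to both groups could remove comparison infants for receiving usual care.

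Most of this stands. A reader might infer that the plan excludes treatment failures; the documents do not support that, and retention is the likelier intent. The reply does not remove the conflict, however. The second-drug line sits in the statistics section beside parental removal and transfer, which item e treats as off-study. Item e's heading covers both treatment failure and participant removal, and its list of other off-study reasons blurs the two again. Section G itself continues only the maternal assessments, so retention of infant data rests on one sentence in item e.

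A reader might also infer that 25 counts successes only, so that 25/0.80 = 31.25 (32) to 25/0.60 = 41.7 (42) infants must be enrolled. The 13 + 12 review schedule and the sample-size limit in Section 7.d contradict this.

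Two further limits are fair. Section 6.c gives no formal test against the historical data, so bias there touches a descriptive comparison. The study also calls itself a feasibility study, but it sets a powered comparison of LOS as its primary analysis, and that comparison needs a defined population.

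**Conclusion.** The point holds as an unresolved conflict in the text, with possible rather than certain bias. Applied literally, the Accrual definition and the second-drug line can drop methadone infants who by rule lose early discharge. Item e and the treatment-based objectives point the other way, and Section 6.c does not choose.

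The actual size cannot be determined from the documents. The 0.8-1.6 and 1.4-2.8 day figures are illustrations that rest on 20-40% applying to the 25 treated methadone infants and on the assumptions in step 5 of the working. They are smaller than the planned 4-day difference, and smaller than the hypothesised fall from 25 to under 15 days, but large enough to matter beside the former. A bias in favour of methadone against the concurrent group should not be taken as settled, because it requires that adjunct-treated comparison infants be kept. The plan should be corrected before LOS is analysed.

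**What to change.** 1. In Section 6.c, state that all enrolled infants who start pharmacologic treatment are analysed for LOS in their own group, whatever adjunct therapy or readmission follows, and that only the screen failures already defined are left out. This applies to both groups.
2. Replace the second-drug line under Early stopping rules with a cross-reference to the Off-treatment Criteria (G), saying that such an infant leaves the home-discharge pathway but not the analysis.
3. In Accrual, state that the definition of infant participants is not the analysis set.
4. Define LOS for readmitted infants: report the first stay and total hospital days to final discharge, and name one as primary.

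The cost is a wording amendment. No new procedure is needed: item e already collects data to final discharge, and comparison-group data come from the medical record. The downside is that the methadone LOS estimate may be less favourable.
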